# **PROTOCOL SYNOPSIS**

Protocol Number	21-001			
Study Title	Fl owTriever Pulmon ary Embolectomy Clinical Study- F low T riever 2 (FLARE-FT2)			
Study Device	FlowTriever2 Catheter			
Regulatory Status	
 
Under US Regulations 510(k) number K201541, the FlowTriever2 Catheter is indicated for:         
 
The non-surgical removal of emboli and thrombi from peripheral blood vessels.
 
Injection, infusion, and/or aspiration of contrast media and other fluids into or from a blood vessel.
 
 
 
The FlowTriever2 Catheter is intended for use in the peripheral vasculature.
 
			
Sponsor	Inari Medical [name]			
Study Objective	The primary study objective is to evaluate the safety and effectiveness of the FlowTriever2 Catheter for the treatment of pulmonary embolism (PE).			
Study Population	This study will enroll 50 subjects			
Number of Sites	Five to twelve (5-12) sites will participate in the study			
Study Design	The FLARE-FT2 confirmatory study is a prospective, single-arm, multicenter study of the FlowTriever2 Catheter			
Safety Endpoints	
 
The study's primary safety endpoint is incidence of adjudicated Serious Adverse Events (SAE), which is a composite of:         
 
Mortality through 48 hours after the index procedure related to FlowTriever2 Catheter
 
Major bleeding through 48 hours after the index procedure related to FlowTriever2 Catheter
 
Intra-procedural device or procedure-related adverse events, including:

			

	The study's primary effectiveness endpoint is the change in mean pulmonary arterial pressure from baseline pre-procedure and post-procedure  The study's secondary effectiveness endpoints are:  The change in systolic pulmonary arterial pressure from baseline pre-procedure to post-procedure  Incidence of adjunctive thrombolytic use				
Effectiveness Endpoints					

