# 4.4 SECONDARY ENDPOINTS - SAFETY

The study's secondary safety endpoints will include incidence of adjudicated Adverse events, including:

- All-cause mortality through the 30-day visit (visit window = 30 days from procedure -5 / +15 days)
- Device-related SAE through the 30-day visit (visit window = 30 days from procedure -5 / +15 days)
- Symptomatic recurrence of pulmonary embolism through the 30-day visit (visit window = 30 days from procedure
   -5 / +15 days)

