## 8.4 EVENT RELATIONSHIP

The Investigator will categorize the relationship of the adverse event as follows:

- **Study Disease-related:** Event is clearly attributable to underlying disease state with no temporal relationship to the device, treatment or medication.
- **Concomitant Disease-related:** Event is attributable to disease other than the study disease with no temporal relationship to the device, treatment or medication.
- **Procedure-related:** Event has a strong temporal relationship to the procedure or treatment with the device deployment or any user handling.
- **Device-related:** Event has a strong temporal relationship to the device and alternative etiology is less likely.
  - Primary Study Device: FlowTriever2 Catheter

FLARE-FT2 Study CONFIDENTIAL Page 41 of 60

- Ancillary Device: Any device other than the FlowTriever2 Catheter, such as the Triever Catheter, a
  guidewire, pressure monitoring catheter, or infusion catheter
- o **Device Unknown:** Device-related but unable to attribute a specific device relationship
- **tPA-related:** Event is clearly attributable to tPA medication with no temporal relationship to the device or treatment.
- Unrelated to the above categories: Event has no relationship to any of the above-mentioned categories.
- **Unknown:** Event relationship is not known or unsure.

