# 12 TERMS AND DEFINITIONS

Term	Definition	
	Primary Safety Definitions	
Clinical Deterioration	Clinical deterioration will include treatment-related events, such as unplanned endotracheal intubation, unexpected requirement for mechanical ventilation, arterial hypotension (>1 hour or requiring vasopressors) or shock, cardiopulmonary resuscitation, persistent worsening in oxygenation, and emergency surgical embolectomy.	
Device Related Death	Device-related death is defined as any death directly related to thedevice not performing as expected. Device-related death would include death from:  Vascular or cardiovascular injury  Device malfunction  Device-induced cardiac arrhythmia	
Life Threatening or Disabling Bleeding (VARC-2)	
 
Fatal bleeding, OR
 
Bleeding in a critical organ, such as intracranial, intraspinal, intraocular, or pericardial necessitating pericardiocentesis, or intramuscular with compartment syndrome, OR
 
Bleeding causing hypovolemic shock or severe hypotension requiring vasopressors or surgery, OR
 
Overt source of bleeding with drop in hemoglobin ≥5 g/dL or whole blood or packed red blood cells (RBCs) transfusion ≥ 4 units*
 
	
Major Bleeding (VARC- 2)	Overt bleeding that is:  Associated with a drop in the hemoglobin level of at least 3 g/dL, OR  Requires transfusion of 3 units of whole blood/RBC, OR  Causes hospitalization, permanent injury, or requiring surgery, AND  Does not meet criteria of life-threatening or disabling	
Minor Bleeding (VARC- 2)	Any bleeding worthy of clinical mention (e.g., access site hematoma) that does not qualify as life-threatening or disabling bleeding or major bleeding.	
Pulmonary Vascular Injury	Pulmonary vascular injury is defined as perforation or injury of a major pulmonary arterial branch during the index procedure requiring intervention, including but not limited to blood transfusion, open or endovascular intervention, to avoid permanent injury.	
Cardiac Injury	Cardiac injury is defined as any damage to the heart during the index procedure requiring intervention, including but not limited to blood transfusion, open or endovascular intervention, to avoid permanent injury.	
Additional Definitions		

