ESC	European Society of Cardiology
FAS	Full Analysis Set
FLARE	FlowTriever Clinical Embolectomy Clinical Study
FT2	FlowTriever2 Catheter
HIT	Heparin-induced thrombocytopenia
INR	International normalized ratio
IRB	Institutional Review Board
ISS	Injury Severity Score
ITT	Intent-To-Treat
LV	Left ventricle
MAE	Major adverse event
MITT	Modified Intent-To-Treat
PE	Pulmonary embolism
PESI	Pulmonary Embolism Severity Index
RV	Right ventricle
RV/LV	Right ventricular to left ventricular diameter ratio
SADE	Serious Adverse Device Effect
SAE	Serious Adverse Event
SBP	Systolic Blood Pressure
SIR	Society of Interventional Radiology
SPESI	Simplified Pulmonary Embolism Severity Index
TLF	Tables, lists, and figures
UADE	Unanticipated Adverse Device Effect
USADE	Unanticipated Serious Adverse Device Effect
VARC-2	Valve Academic Research Consortium-2

1. Description of Study Objectives

The primary study objective is to evaluate the safety and effectiveness of the FlowTriever2 Catheter for the treatment of acute pulmonary embolism (PE).

2. Study Design

The study is a prospective, non-randomized, single-arm, multicenter, observational study to evaluate the safety and effectiveness as the study endpoints of the FlowTriever2 Catheter in patients eligible for endovascular treatment of acute PE. The endpoints will be evaluated in descriptive manner and will not be used to determine study success.

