5.1. Sample Size

The sample size of 50 subjects was adopted to confirm the FlowTriever2 Catheter performance. Given the sample size, at least 80% power can be achieved under one-sample fixed design with one-sided alpha = 0.05 for assuming observed FT2 safety event proportions of 11% compared to the hypothesized performance goal of 25% from FLARE. Descriptive statistics on safety and effectiveness endpoints will be provided based on all subjects to conclude the study objectives, no hypothesis testing was relied. Sensitivity analysis will be performed on a sub-population of the 50 subjects that did not receive adjunctive thrombolytics.

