5.2. Primary Safety Endpoint Analysis

The primary safety endpoint analysis is performed by assessing the incidence rate of the composite endpoint of SAE, including device-related mortality through 48 hours, device-related major bleeding through 48 hours, intra-procedural device or procedure-related adverse events.

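### The primary safety composite counts major bleeding only, a tier defined to exclude life-threatening or disabling bleeding, so a survived device-related catastrophic bleed after the procedure can be left out of the primary rate

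*Protocol*

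**What the plan says.** The bleeding component is worded the same way in the Protocol Synopsis, Protocol sections 4.2 and 9.3, and SAP section 2.1: "Major bleeding through 48 hours after the index procedure related to FlowTriever2 Catheter". SAP section 5.2 restates it as "device-related major bleeding through 48 hours". No other component of the composite is a bleeding endpoint.

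Protocol section 12 and SAP section 6 give three VARC-2 bleeding tiers under the heading for primary safety definitions.

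- **Life-threatening or disabling** includes, among other criteria, "Bleeding in a critical organ, such as intracranial, intraspinal, intraocular, or pericardial necessitating pericardiocentesis", and also a hemoglobin drop of 5 g/dL or more or a transfusion of 4 units or more.
- **Major** requires a drop of at least 3 g/dL, or a 3-unit transfusion, or a bleed that causes hospitalization or permanent injury or needs surgery. After the word AND it adds "Does not meet criteria of life-threatening or disabling".
- **Minor** is whatever qualifies for neither of the two higher tiers.

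The SAP's study design section says of the endpoints: "The endpoints will be evaluated in descriptive manner and will not be used to determine study success". SAP section 5.1 adds that "no hypothesis testing was relied". Protocol section 4.4 lists the secondary safety endpoint "Device-related SAE through the 30-day visit".

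**The concern.** Where bleeding tiers exclude one another, an endpoint that names only the middle tier does not pick up the top one. As written, the composite can count a less severe bleed and omit a more severe one, so the headline safety rate can understate harm.

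This matters for the device's rationale. Protocol section 1.6.5 expects mechanical removal to keep the bleeding complications of thrombolysis to a minimum. Sections 1.6.3 and 1.6.6 single out intracranial hemorrhage as a risk of lytic treatment. Section 7.3.1 says that patients at high risk of catastrophic bleeding are not excluded. The primary safety rate is where a reader would look for exactly these events.

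**Working it through.** **The plan's own figure.** Protocol section 9.1 and SAP section 5.1 claim at least 80% power with N = 50, an assumed rate of 11%, a performance goal of 25% and one-sided alpha of 0.05. In the exact binomial test, the largest c with P(X ≤ c | 50, 0.25) ≤ 0.05 is c = 7, which has an exact alpha of 0.0453. Power is P(X ≤ 7 | 50, 0.11) = 0.821. The figure reproduces, and the sample size is not in question here.

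**Test case.** Take a non-fatal intracranial bleed 24 hours after the procedure, adjudicated as FlowTriever2-related, with no 3 g/dL drop and no 3-unit transfusion. It meets the critical-organ criterion of the life-threatening tier. Set it against each component:

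| Component | Does the bleed count? |
|---|---|
| Device-related death to 48 h | No, the subject survived |
| Major bleeding, AND clause applied to all criteria | No, the clause excludes it |
| Major bleeding, AND clause applied to the last criterion only | No. The clause blocks the last criterion, and the hemoglobin and transfusion criteria are not met |
| Clinical deterioration | No, it is listed under intra-procedural events |
| Pulmonary vascular injury, cardiac injury | No, wrong site and not during the index procedure |

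The bleed is therefore omitted on either reading of the AND clause. A device-related bleed at the same time with a 3 g/dL drop, and no feature of the higher tier, does count.

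**How wide the gap is.** If the clause governs only the last criterion, a drop of 5 g/dL or more also satisfies the 3 g/dL criterion and is counted. If it governs all criteria, that bleed is excluded too. The residual definition of minor bleeding treats the tiers as separate categories, which favors the exclusive reading. Some severe bleeds enter by other components whichever reading applies: device-related death, intra-procedural deterioration, or vascular or cardiac injury.

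**Size.**

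- Effect per omitted subject: 1/50 = 2.0 percentage points.
- Scale: at FLARE's 3.8% (Protocol section 3.1), the expected count is 50 × 0.038 = 1.9 subjects, so one omission is large in relative terms.
- Example with exact (Clopper-Pearson) 95% intervals: 3/50 = 6.0% (1.3% to 16.5%) would be reported as 2/50 = 4.0% (0.5% to 13.7%).
- Chance of at least one such bleed in 50 subjects is 1 − (1 − p)^50. The documents give no p, so these values are assumptions:

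| Assumed p per subject | Chance of at least one in 50 |
|---|---|
| 0.2% | 9.5% |
| 0.5% | 22.2% |
| 1.0% | 39.5% |

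For context on p, FLARE had one major bleed among 106 subjects (0.9%) and the FLASH interim had three among 250 (1.2%). Those are rates for all bleeds called major in those studies, so 1% for this narrow subset is a generous upper end.

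**Against the 25% goal used for sizing.** The exact one-sided 95% upper limit is 24.7% for 7/50 and 27.0% for 8/50. One omission could move a descriptive comparison across 25%, but only near that count, and no success rule uses it.

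**The case against.** The strongest objection is that very few events are affected. The bleed must be attributed to the FlowTriever2 Catheter itself, survived, post-procedural and in the top tier. Protocol section 8.4 requires that another cause be less likely, and these patients are anticoagulated, so an intracranial bleed would seldom be attributed to the catheter. Bleeds the catheter could plausibly cause, such as pulmonary artery or cardiac perforation, have their own components. Section 8.4 also has a separate ancillary category, "Any device other than the FlowTriever2 Catheter, such as the Triever Catheter", which would take many access-site bleeds. FLARE reported no device-related major adverse events, and its one major bleed was also a vascular injury and a clinical deterioration.

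A second objection is that little depends on the rate. No test or success rule uses it, and the event would still be reported as a device-related SAE. A third is that the Clinical Events Committee charter, which is not among the documents, may say which tiers count, and that listing the top tier among the primary safety definitions hints that it was meant to. The protocol's account of the FLASH interim describes its events as major bleeds other than intracranial hemorrhage, which suggests that the registry's term can cover intracranial bleeds.

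What stands: the gap is narrow, the upper assumed rate is generous, and loose drafting is as likely an explanation as deliberate exclusion. None of this closes the gap. An unseen charter cannot be assumed to override the endpoint definition. The listing is only suggestive, since minor bleeding is listed there too. The secondary endpoint means the event is misplaced rather than lost. Bleeds attributed to another device, the procedure or tPA fall outside the component because of the relatedness condition, which this point does not challenge.

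**Conclusion.** The concern holds. Following both documents as written, the primary safety rate can leave out a survived, FlowTriever2-related, life-threatening bleed after the procedure while counting a less severe one. The size is 2 percentage points per omitted subject, set against roughly two expected events if the FLARE rate applies. How often it would happen is unknown, and the 9.5% to 39.5% range rests wholly on assumed rates.

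The consequence is a descriptive rate that can understate harm. No pass or fail decision is affected. Whether the rate is like for like with FLARE or FLASH cannot be checked, because the documents do not give those studies' bleeding definitions. The endpoint should still be corrected: its wording produces the wrong ordering of severity, and the correction is cheap.

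**What to change.** In the Protocol Synopsis, Protocol sections 4.2 and 9.3, and SAP sections 2.1 and 5.2, word the component as: Major, life-threatening or disabling bleeding (VARC-2) through 48 hours after the index procedure related to FlowTriever2 Catheter. Leave the relatedness condition as it is, and report the two tiers separately beneath the composite. Make the change before adjudication and analysis, since reclassifying a bleed after it has occurred would look data-driven.

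The cost is a short amendment at five places in two documents, IRB approval of the protocol change (Protocol section 10.1.1), and alignment of any charter or eCRF wording tied to the component. No new data are needed: both tiers are already defined and the Clinical Events Committee already adjudicates all adverse events (Protocol section 8.7). N = 50 does not change, and the 82.1% power is unaffected if the assumed 11% already covers these bleeds. The reported rate may be slightly less favorable.

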# 6.2.1 BASELINE

Baseline assessments will include the following:

- Verification of inclusion/exclusion criteria
- Medical history
- Physical examination/vitals
- Blood labs
- CT angiography to confirm PE and RV/LV ratio for inclusion
- Concomitant medications

**Medical/Surgical History:** Relevant medical and surgical history will be collected from all consented subjects at the time of enrollment.

**Blood Labs**: The following blood values must be available to assess Subject eligibility for the study and for baseline data collection: hematocrit, hemoglobin, platelet count, serum creatinine, and International Normalized Ratio (INR).

**Concomitant Medications**: It is required that the subject's relevant concomitant medication use during the study be documented at pre-procedure, procedure, and follow- up visits.

FLARE-FT2 Study CONFIDENTIAL Page 31 of 60

\*\*Day 0 is the date of the FlowTriever procedure, Time 0 is when the FlowTriever2 Catheter enters the vasculature

\*\*\* Anticoagulation and Thrombolytics

\*\*\*\*If discharged prior to 48 hours from Index Procedure, phone call to subject will be conducted to confirm if any SAEs occurred between time of discharge and 48 hours.

As part of the routine care to treat PE, anticoagulation medication is administered to impede blood clotting and thrombolytic medication may be administered to dissolve blood clots. The specific dose and course of administration is at the discretion of the Investigator and will be recorded on the case report form (CRF).

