	pulmonary embolism (one of the following clinical manifestations at presentation). 1.
	Cardiac Arrest: Need for cardiopulmonary resuscitation, 2. Obstructive Shock: Systolic
	BP < 90 mmHg or vasopressors required to achieve a BP ≥ 90 mmHg despite adequate
	filling status AND End-organ hypoperfusion (altered mental status; cold, clammy skin;
	oliguria/anuria; increased serum lactate), OR 3. Persistent Hypotension: Systolic BP <
	90 mmHg or systolic BP drop ≥ 40 mmHg, lasting longer than 15 min and not caused by
	new-onset arrhythmia, hypovolemia, or sepsis.
Intermediate High-Risk	Per ESC guidelines 2019: Intermediate High-Risk PE determined by no hemodynamic
PE	instability, PESI III- V or sPESI ≥ 1, RV Dysfunction, and Elevated cardiac troponins.
Intermediate Low-Risk	Per ESC guidelines 2019: Intermediate Low-Risk PE determined by no hemodynamic
PE	instability, PESI III- V or sPESI ≥ 1, and 1 or none of the following: RV Dysfunction;
	Elevated cardiac troponins.
Patient/ Subject	Participants in the study.
Recurrent PE	Symptomatic worsening from baseline of the embolism that was successfully treated
	with the index procedure with documentation of a change on CTPA or other suitable
	imaging modality, as determined by the CEC.

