5.4. Secondary Safety Endpoint Analysis

The secondary safety endpoint analysis is performed by assessing the incidence rates of adjudicated adverse events, including all-cause mortality through the 30-day visit, device-related SAE through the 30-day visit, and symptomatic recurrence of pulmonary embolism through the 30-day visit.

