High-Risk PE	
Per ESC guidelines 2019: High-Risk PE determined by hemodynamic instability, PESI III-V or sPESI ≥ 1, RV Dysfunction, and Elevated cardiac troponins.
 
Note Definition of hemodynamic instability, which delineates acute high-risk pulmonary embolism (one of the following clinical manifestations at presentation). 1. Cardiac Arrest: Need for cardiopulmonary resuscitation, 2. Obstructive Shock: Systolic BP < 90 mmHg or vasopressors required to achieve a BP ≥ 90 mmHg despite adequate filling status AND End-organ hypoperfusion (altered mental status; cold, clammy skin; oliguria/anuria; increased serum lactate), OR 3. Persistent Hypotension: Systolic BP < 90 mmHg or systolic BP drop ≥ 40 mmHg, lasting longer than 15 min and not caused by new-onset arrhythmia, hypovolemia, or sepsis.

Intermediate High-Risk PE	
Per ESC guidelines 2019: Intermediate High-Risk PE determined by no hemodynamic instability, PESI III- V or sPESI ≥ 1, RV Dysfunction, and Elevated cardiac troponins.

Intermediate Low-Risk PE	
Per ESC guidelines 2019: Intermediate Low-Risk PE determined by no hemodynamic instability, PESI III- V or sPESI ≥ 1, and 1 or none of the following: RV Dysfunction; Elevated cardiac troponins.

Patient/ Subject	
Participants in the study.

Recurrent PE	
Symptomatic worsening from baseline of the embolism that was successfully treated with the index procedure with documentation of a change on CTPA or other suitable imaging modality, as determined by the independent Medical Monitor.

Signature Page for VV-TMF-35809 v1.0

Reason for signing: Approved	Name: [name] Role: Approver Date of signature: 06-Sep-2023 13:43:37 GMT+0000
Reason for signing: Approved	Name: [name] Role: Approver Date of signature: 06-Sep-2023 15:15:32 GMT+0000
Reason for signing: Approved	Name: [name] Role: Reviewer Date of signature: 06-Sep-2023 18:22:33 GMT+0000
Reason for signing: Approved	Name: [name] Role: Approver Date of signature: 07-Sep-2023 13:13:07 GMT+0000

Signature Page for VV-TMF-35809 v1.0

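### Read literally, the recurrent-PE definition leaves new emboli, and new PE after an unsuccessful procedure, out of the secondary recurrence endpoint, and the two documents name different adjudicators

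*Protocol*

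**What the plan says.** Protocol 4.4 lists among the secondary safety endpoints "Symptomatic recurrence of pulmonary embolism through the 30-day visit". Protocol 9.5 and SAP 2.3 repeat it. SAP 5.4 gives the analysis: "The secondary safety endpoint analysis is performed by assessing the incidence rates of adjudicated adverse events", with recurrence as one of the three items.

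The term is defined once in each document. Protocol section 12 reads "Symptomatic worsening from baseline of the embolism that was successfully treated" and continues "with the index procedure with documentation of a change on CTPA or other suitable" imaging, as decided by the CEC. The Terms and Definitions table in SAP section 6 has the same criterion, "Symptomatic worsening from baseline of the embolism that was successfully treated with the index procedure", but gives the decision to a different body: "as determined by the independent Medical Monitor". Neither document mentions new emboli, emboli in other arteries, or how to treat subjects whose procedure did not succeed.

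Neither section 12 nor SAP section 6 defines baseline or successful treatment. The effectiveness endpoints in Protocol 4.1 and 4.3 use baseline for the pre-procedure state. The only CTA in the schedule (Protocol 6.2, Table 1) is the baseline one, described in Protocol 6.2.1 as "CT angiography to confirm PE and RV/LV ratio for inclusion".

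**The concern.** The endpoint's name promises a count of symptomatic PE recurrences. The definition restricts the count to deterioration of one particular embolism, the one treated successfully. A new clot that travels to a different artery is what most readers would call a recurrence, and on a literal reading it does not qualify.

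The Protocol's own background uses the term in the wider sense. Section 1.6.3 sets recurrent PE against emboli already present, and section 1.6.1 separates recurrent embolic events from propagation of existing thrombus. The definition then counts only the existing embolus. Section 7.3 also suggests that aspiration lowers the chance of re-thrombosis and of new emboli. The plan's only recurrence endpoint, as written, cannot speak to the second of these.

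At stake is whether a reported recurrence rate, possibly zero, means what a reader will take it to mean. Because the study relies on description rather than testing, what each endpoint counts is its whole information content.

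**Working it through.** The plan states no recurrence rate or target, so there is no figure of its own to reproduce. The check sets the wording against the kinds of event that could occur.

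**Elements of the definition** (Protocol 12; same criterion in SAP 6)
1. Symptoms worse than baseline.
2. The worsening is of the embolism that was treated.
3. That treatment was successful.
4. A change is documented on CTPA or other suitable imaging.

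**Events against the elements, read literally**

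| Event by the 30-day visit, with symptoms and imaging | Element not met | Counted? |
|---|---|---|
| New embolus in another artery, index procedure successful | 2 | No |
| New PE, index procedure unsuccessful | 3, and 2 if the clot is elsewhere | No |
| Re-occlusion at the treated site, worse than before the procedure | None | Yes |
| Re-occlusion at the treated site, worse than after the procedure but no worse than before it | 1, if baseline means pre-procedure | Unclear |
| Unresolved original clot after an unsuccessful procedure | 3 | No, and rightly: this is persistence, not recurrence |

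The fourth row is unclear for two reasons. Baseline is not defined where the term is used, although Protocol 4.1 and 4.3 use it for the pre-procedure state. Also, the comparison with baseline attaches to the symptoms; the imaging clause asks only for a change and does not name the reference image.

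The second row can arise in the analysed subjects. The ITT set in Protocol 5.3 includes deployments regardless of success, and SAP 5.1 bases the descriptive statistics on all subjects.

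**Where an uncounted event would still appear.** Protocol 8.7 has the CEC adjudicate all adverse events, so a new PE remains in the data. Within the secondary safety endpoints it appears elsewhere only if it is fatal (all-cause mortality) or a device-related SAE. A non-fatal new embolus not attributed to the device appears in neither, and SAP 5.2 to 5.5 specify analyses only for the named endpoints.

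**Size per event.** With the planned 50 subjects as denominator (Protocol 5.1), one event is 1/50 = 2.0 percentage points. The event counts below are assumptions, with exact (Clopper-Pearson) 95% intervals:
- 0/50 = 0%, interval 0 to 7.1%
- 1/50 = 2%, interval 0.05 to 10.6%
- 2/50 = 4%, interval 0.5 to 13.7%

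If two real recurrences were both new emboli, the endpoint would read 0% instead of 4%.

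**What the documents offer on frequency.** Protocol 3.4 reports 30-day data on 242 FLASH subjects with 13 readmissions, one of them related to the acute PE: 1/242 = 0.4%, or 50 × 1/242 = 0.2 subjects in a study of 50. This is a weak proxy, since it omits recurrences during the index stay and any that did not lead to readmission. The same section reports concomitant DVT in 68.4%. That makes new emboli plausible, but it is not a recurrence rate.

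**The case against.** The strongest case for leaving the definition alone has four parts.

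*Embolism may mean the disease episode, not one clot.* Protocol 2.2 and 5.3 use the word that way, and the endpoint's name is broad. On that reading a new embolus could be taken as worsening of the PE. The reading is possible, but less natural where the text speaks of the embolism treated by the index procedure. If both readings are open, the same event can be classified two ways, which is itself a reason to clarify.

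*Nothing is lost.* This stands as far as the data go: the events are adjudicated as adverse events. It does not put them into this endpoint. Naming an adjudicator does not widen the written criterion. The CEC Charter may hold fuller criteria, but it is not among the documents, and the SAP names a different body.

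*Requiring success is partly sensible.* This also stands. Clot that was never cleared has not recurred, so the criticism is limited to a truly new PE after an unsuccessful procedure. That may affect few subjects, since Protocol 1.6.6 says full clearance is not the aim.

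*The endpoint decides nothing.* SAP section 2 says the endpoints are descriptive and do not determine study success, SAP 5.1 relies on no hypothesis test, and no comparison of recurrence rates is planned. This limits the weight of the point but does not remove it.

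A reader might also infer that all re-embolisation after clot removal is excluded, or that the endpoint is driven to zero by a known amount. The documents support neither. Re-occlusion worse than baseline still counts, and no expected rate is given.

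**Conclusion.** The point holds in a limited form. On a literal reading, the definition in both documents leaves out a new symptomatic embolus in another artery and a new PE after an unsuccessful index procedure. For re-occlusion at the treated site, the problem is an unspecified reference state, not a settled exclusion.

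The consequence is a possible downward error in one descriptive secondary safety endpoint, at 2 percentage points per missed event if the denominator is 50. The total cannot be computed. The primary endpoints, the sample size and the stated power are unaffected. The conclusion assumes that adjudication follows the written definition and that no document outside those reviewed replaces it.

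The disagreement over who decides, the CEC in Protocol 12 and the independent Medical Monitor in SAP 6, holds on either reading and has to be reconciled. The whole is worth correcting before the recurrence endpoint is adjudicated, because the remedy is wording only.

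**What to change.** Put the same definition in Protocol 12 and SAP 6:
- **Event:** new or worsening PE symptoms after the index procedure, with a new or extended filling defect in any pulmonary artery, whether or not the index procedure succeeded.
- **Reference:** the most recent available imaging, whether the pre-procedure CTA, the end-procedure angiogram or a later CT.
- **Guard:** residual or distal clot already present or expected after the procedure does not count as new. Protocol 1.6.6 anticipates such clot, and a later CT may show clot that an angiogram did not.
- **Adjudicator:** one named body in both documents.

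The cost is a short aligned passage in each document. No scheduled imaging is added, because the present definition already requires imaging documentation, and Protocol 6.2.2 already has the Investigator review the images after the procedure. Events already recorded can be reclassified, since all adverse events are adjudicated.

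There are two downsides. The reported rate may be slightly higher. And because Table 1 schedules no post-procedure CT, some events will need adjudicator judgment to separate residual from new clot.
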